2.3.2 Inclusion Criteria

Women who meet the following criteria will be eligible for the study:

- 1) Postpartum women
- 2) Antepartum diagnosis of hypertension, defined as existing chronic hypertension diagnosis or documented blood pressure of ≥ 140 systolic OR ≥ 90 diastolic on at least 2 occasions at least 4 hours apart prior to delivery
- 3) At least 18 years of age
- 4) English or Spanish speakers

2.3.3 Exclusion Criteria

- 1) Non-English or Spanish speakers
 - The consent form will only be available in these 2 languages
- 2) Lives outside of NY State, unless their physician is licensed in the state of residence
 - The telemedicine laws in NJ prohibit physicians from practicing telemedicine unless licensed in NJ; the NYP legal team is investigating if this is true for other states
- 3) Women who are not planning on obtaining their postpartum follow up at CUIMC
- 4) Women who are physically unable to hold or use the tablet
- 5) Women who do not have a working phone
- 6) Women whose obstetric providers are unable or unwilling to implement escalation pathways
- 7) Women who were diagnosed with hypertension postpartum

2.3.4 Recruitment, Screening and Enrollment

We will use a recruitment strategy designed and utilized by the OB department. An OB research coordinator (RC) will perform daily chart screen of all women admitted to the CUIMC postpartum unit (CHONY 5 central, 6 central and 10 central). Permission from healthcare providers will be obtained prior to the OB RC contacting participants. Eligible women will then be recruited from the aforementioned postpartum units. After obtaining written informed

consent, participants’ sociodemographic characteristics will be collected. Information regarding their diagnosis of HDP and delivery information will be collected at that time as well. They will then be randomized to either usual care, as defined above, or the study group. Randomization will occur in REDCap. Those in the study group will be educated on use of the Philips equipment by research personnel who will have been educated on use of the equipment, with support over the phone by a Philips representative. Nursing staff will be familiarized with the equipment as well, and will be available to answer any questions the patient might have. Patients in the study group will be provided with the Philips telehealth kit, complimentary of participating in the study, prior to being discharged from the hospital (see “Equipment and Software” section, below). Their chart will be created in the eCC prior to discharge from the hospital by the RC.

Once home, the patient will receive a “Welcome Call” from a Philips representative, which will ensure that the equipment is set up properly and that all the patient’s questions are answered. If the patient has any remaining difficulty with equipment, Philips will arrange for a home visit from a representative, which will occur within 72 hours. Prior to that visit, if the Bluetooth system is not working properly, the cuff will still work as a normal blood pressure cuff, so the patient will be able to take measurements.

2.3.5 Equipment and Software

The usual care group will be given a prescription for a blood pressure cuff. In general, the prescription does not specify a model of cuff; this is up to the discretion of the pharmacist or the patient.

The study group will receive a Philips Home Telehealth Solution kit, complimentary of participating in the study, which includes several FDA/FCC approved devices. NewYork-Presbyterian has a contract in place with Philips (attached separately to this IRB application under “Philips Contract 5.30”) which allows the hospital to utilize Philips telehealth programs for its patients. **The investigators had no role in the signing of this contract and have no financial interests in this program.** The following equipment is included in the Philips kit:

Device	US 510(k)
A&D Blood Pressure Meter, regular or small cuff version UA-767PBT-Ci	Class II K043217 FCC:POOWML-C40
eCareCoordinator (eCC) Suite	K171029
Samsung Galaxy Tab E 8.0" model SM-T377A	Not a medical device, no associated 510(k) FCC: A3LSMT377A

The instructions that patients will receive for use of the tablet and the blood pressure meter are attached separately to this IRB application (“Philips patient instructions”/ ”A&D Cuff Instructions”).

The eCC Clinical User Guide is also attached separately to this IRB application (“eCC Clinical User Guide for Version 1.6”). It outlines the use of the applications contained within the eCC Suite for both patients and providers, including the metrics that can be collected for each patient.

The most relevant components of this document are listed below. The page numbers listed refer to the page number within the PDF document and not the page number found in the bottom right corner of each page.

- Patients view (p.24-25): describes the columns of information that are available for review and analysis
- Overall score/flag values (p.27-29): describes how clinical data is flagged for review
- Hospital admissions/ED visits (p.73-76): describes how hospital admissions and ED visits are tracked within the patient chart.
- Calendar (p.79-80): illustrates the patient tasks expected each day in a calendar format. These tasks may include surveys, measurements, clinician tasks, appointments and sticky notes.
- Surveys (p.86-89): describes how surveys are displayed as part of the calendar and how they can be accessed. The surveys that will be available as part of this study are attached as a separate document to this IRB application (“Surveys”). They include:
 - Preeclampsia Symptom Survey-scheduled
 - Preeclampsia Symptoms Survey-reflexive, high acuity
 - Preeclampsia Symptoms Survey-reflexive, low acuity
 - Medication Survey
 - Satisfaction Survey-Program Start (*will also be given to the control group*)
 - Satisfaction Survey-Program End (*will also be given to the control group*)
 - Telemedicine Survey Specific-Program End
- Measurements (p.91-92): describes how patient measurements are displayed and scheduled. **For this study, only blood pressure and heart rate will be measured.**
- Patient issues (p.128-137): describes how acute conditions that affect daily patient care activities are monitored and how chronic problems are tracked.
- Reviewing flags and issues (p.142-146): describes how patients are flagged for clinical assessment and intervention, and how these flags and issues are reviewed and addressed
- Intervention rules (p.188- 210): conditional statements that consist of a condition and an action that the system will trigger when the condition is met. **The intervention rules for this study are attached to the IRB application as a separate document (“HDP calendar and intervention rules”) and workflows can be found as a separate document as well (“Workflows”).**

At the conclusion of the 6-week study period (in other words, after the scheduled postpartum visit or the time when that visit was supposed to occur, if the patient did not present), the patient

will be expected to return the kit. The full patient terms of use are attached to this IRB application as a separate document (“Philips Terms of Use”).

2.3.6 Outcomes

- 1) **Primary outcome:** Our primary outcome will be percentage of the recommended twice daily blood pressures reported between hospital discharge and outpatient blood pressure assessment.
- 2) **Secondary outcomes:** Secondary outcomes will include:
 1. Percentage of recorded blood pressure values during that time frame that are elevated (>140 systolic OR >90 diastolic)
 2. Percentage of elevated blood pressures that triggered a phone call to an obstetric provider
 3. Rate of attendance at outpatient blood pressure assessment
 4. Incidence of elevated blood pressure at the outpatient blood pressure assessment
 5. Rate of outpatient assessment for postpartum care
 6. Incidence of elevated blood pressure at the postpartum assessment
 7. Time to initiation of antihypertensive medications (in patients who were not on medications at time of discharge) and adjustment of antihypertensive medications
 8. Final dosage of antihypertensive medications at 6 weeks postpartum
 9. Readmission rate
 10. Rate of emergency department visits
 11. Rate of HDP-associated morbidities (e.g.: stroke, seizure, PRES)
 12. Percentage of patients who require a referral to primary care physicians after being discharged from obstetric care at the postpartum visit
 13. Patient satisfaction with the method, to be assessed via a validated clinical survey (attached separately in the document entitled “Surveys”).

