2.3. Methods

2.3.1 Study Design

This will be a randomized control trial, in which women with HDP diagnosed prior to delivery will be assigned to either usual care or to a telehealth kit that, supplied by Philips. New York Presbyterian has a contract in place with Philips (attached separately to this IRB application under “Philips Contract 5.30”) which allows the hospital to utilize Philips telehealth programs for its patients. The telehealth kit will include a Bluetooth-enabled blood pressure cuff which is FDA approved to monitor blood pressure as well as pulse, and a tablet that includes a clinical monitoring software (eCareCoordinator, or eCC). Further details regarding the devices are outlined in the “Equipment and Software” section below.

Patients will be recruited from the postpartum service. All patients will be asked to check their blood pressure twice per day, once in the morning and once in the evening. Pulse will also be recorded as it is taken automatically at time of blood pressure reading; though this parameter is not being studied, there will be protocols in place to address abnormal values. Control group patients will use the blood pressure cuff that they procure after discharge using the prescription they are given, and will be asked to keep a log of their blood pressure measurements. Study group patients will use the Philips Bluetooth-enabled blood pressure cuff, which will transmit blood pressure measurements via Bluetooth from the monitor to the eCC. These patients will be educated on the use of and enrolled in the software by Philips representatives (via telephone) and research investigators who have been in-serviced on the devices prior to discharge. The tablets are cellular-enabled, so no wireless connection is needed in the patient’s home.

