1. **Blood pressures.** For the control group, participants will be asked to provide a record of the blood pressures they are recording at home, and the blood pressures from their office visits will be recorded as well. For the study group, participant blood pressures will be stored in eCC, and the blood pressures from any in-person visits will be recorded as well. Percentage of scheduled blood pressure readings that are recorded will be compared between groups. Incidence of elevated blood pressures during this time will also be compared between groups.
 2. **Communication.** Rate of communication between patient and obstetric provider for each abnormal blood pressure measurement will be compared between groups.
 3. **Adherence.** For both groups, rate of presentation for scheduled appointments will be collected. For the study group, eCC will collect patient reports of reasons why they were unable to check their blood pressure or attend a scheduled appointment
 4. **Time to initiation of medications.** For both groups, time to initiation of anti-hypertensive medications will be tracked
 5. **Final plan at 6 weeks.** For both groups, continuing medication regimens at 6 weeks will be collected. Referral to primary care physician will be collected.
 6. **Hospital readmissions.** Hospital readmission for any indication will be collected for both groups
 7. **ED visits.** Presentation to the emergency department for any indication will be collected for both groups
 8. **Maternal morbidity and mortality.** Incidences of eclampsia, stroke, PRES, maternal death and other preeclampsia-associated morbidities will be collected for both groups
 9. **Home Health Services:** information regarding the use of home health services after discharge including referral to home health services, number of visits and blood pressure at those visits will be collected for both groups

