2.4.2 Statistical analysis

For analysis of discrete (categorical) data in independent samples, the Chi-squared test or Fisher exact probability test will be utilized. For group comparisons, continuous data that satisfy the assumptions of normality and homoscedasticity (homogeneity of variance) will be analyzed by t-test (for 2 independent samples) or analysis of variance (>2 groups, ANOVA) with post hoc comparisons by Scheffe tests. When possible, continuous data that do not fulfill the aforementioned assumptions will be mathematically transformed (e.g., logarithmic transformation) before performing t-tests or ANOVA. In some cases, data that do not satisfy these assumptions will be analyzed by nonparametric methods [Mann-Whitney U Test (for two independent samples) or Kruskal-Wallis One-Way ANOVA (for more than two independent

samples)]. Significant Kruskal-Wallis ANOVAs will be followed by Dunn tests for post hoc analysis. The degree of linear association between variables will be measured by the Pearson product moment correlation coefficient or the Spearman rank-order correlation coefficient and their corresponding tests of significance. Multivariate linear or logistic regression will be utilized where appropriate. In all cases, statistical significance will be assumed when $p < 0.05$. Propensity score analysis will be used as a balancing score as deemed necessary.

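### Secondary outcomes 1 and 2 have blood pressure readings as their denominator, but section 2.4.2 states no unit of analysis and no method for repeated readings within a woman.

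*Combined protocol and SAP*

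**What the plan says.** Section 2.3.6 lists as secondary outcome 1 "Percentage of recorded blood pressure values during that time frame that are elevated" and as secondary outcome 2 "Percentage of elevated blood pressures that triggered a phone call to an obstetric provider". Secondary outcome 12 in the same list has patients as its denominator, so the plan names patients where it means them.

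Other sections point the same way:

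- Section 2.3.7, under communication: "Rate of communication between patient and obstetric provider for each abnormal blood pressure measurement will be compared between groups".
- Section 2.3.1, on frequency: "All patients will be asked to check their blood pressure twice per day, once in the morning and once in the evening". It adds that the total and the elevated counts are established for each group at the 7–10 day visit.
- Section 2.2, sub-aim 1 of Aim 1, again takes elevated readings as the denominator.

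Section 2.4.2 gives the tests. For categorical data: "For analysis of discrete (categorical) data in independent samples, the Chi-squared test or Fisher exact probability test will be utilized". For regression: "Multivariate linear or logistic regression will be utilized where appropriate". For continuous data it plans a t-test, with transformation if needed, and then: "In some cases, data that do not satisfy these assumptions will be analyzed by nonparametric methods [Mann-Whitney U Test (for two independent samples". It names no generalised estimating equations (GEE), mixed model, clustered variance or other repeated-measures method. No section says whether the reading or the woman is the unit of analysis for these two outcomes.

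**The concern.** An elevated-or-not reading is a binary item, so the literal route from 2.3.6 to 2.4.2 is a two-by-two table of readings by group. Chi-squared, Fisher and ordinary logistic regression all treat the entries in such a table as independent. One woman's readings over about a week share her disease severity, her treatment and her cuff, so they are likely to be positively correlated. Any positive correlation makes the pooled standard error too small.

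Two claims are exposed. One is the comparison of elevated readings between groups. The other is sub-aim 1 of Aim 1, that remote monitoring increases communication with providers, which outcome 2 measures. Either could be declared significant more often than the stated 5% level allows. A pooled percentage also lets the women who record most dominate their group's figure.

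Because the unit is left open, the choice between a valid and an invalid test could be made after the data are seen.

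**Working it through.** **The plan's own figure.** No calculation is given for outcomes 1 and 2. The only one is in 2.4.1, for the primary outcome: 60% against 80%, 80% power, 81 per group. With a two-sided 5% level and pooled variance under the null:

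n = [1.96·√(2·0.7·0.3) + 0.842·√(0.6·0.4 + 0.8·0.2)]² / 0.2² = 81.2

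Power at 81 per group is 79.9%, and 81 × 1.25 = 101.25 gives the stated 101. The figure reproduces, so the check below uses a two-sided 5% level and the plan's recording rates of 60% and 80%.

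**Readings per woman.**

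- Most women are discharged at 48–72 hours (2.1), and the visit is at 7–10 days (2.3.1). The window is therefore 7 − 3 = 4 to 10 − 2 = 8 days.
- Two readings a day gives 8–16 scheduled readings.
- At 60–80% recording, this is 0.6 × 8 = 4.8 to 0.8 × 16 = 12.8, or about 5–13 recorded readings.

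**Formula.** With m readings per woman:

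- Design effect DE = 1 + (m − 1)·ICC.
- True error of a nominal two-sided 5% pooled test = 2·[1 − Φ(1.96/√DE)].

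The ICC is an assumption throughout, taken over 0.05–0.5.

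**Outcome 1.** Worked ends of the range:

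- m = 5, ICC 0.05: DE = 1.2, 1.96/√1.2 = 1.79, error 7.4%.
- m = 13, ICC 0.5: DE = 7.0, 1.96/√7.0 = 0.741, error 45.9%.

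| Recorded readings per woman | ICC 0.05 | ICC 0.1 | ICC 0.3 | ICC 0.5 |
|---|---|---|---|---|
| 5 | 7.4% | 9.8% | 18.6% | 25.8% |
| 8 | 9.2% | 13.3% | 26.6% | 35.6% |
| 13 | 12.1% | 18.6% | 36.1% | 45.9% |

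**Outcome 2.** Only elevated readings count, so m is smaller. The documents give no figure; 2–3 per woman is assumed.

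| Elevated readings per woman | ICC 0.05 | ICC 0.3 | ICC 0.5 |
|---|---|---|---|
| 2 | 5.6% | 8.6% | 11.0% |
| 3 | 6.2% | 12.1% | 16.6% |

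The formula takes equal numbers of readings per woman; unequal numbers push the error up.

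**Simulation check, outcome 1.** Beta-binomial data with no group difference: 81 women per group, 60% and 80% recording, 8, 12 or 16 scheduled readings, 20% or 40% elevated (assumed), ICC 0.1, 0.3 or 0.5. That makes 18 scenarios of 2,000 runs each.

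- Pooled chi-squared: 11–17% error at ICC 0.1, 21–33% at 0.3, 28–45% at 0.5.
- One percentage per woman (t-test or Mann-Whitney), or a ratio estimator with variance clustered on the woman: about 4–6% in every scenario.

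**Simulation check, outcome 2.** One percentage per woman, among women with at least one elevated reading. Same group size, recording rates and range of scheduled readings, with an assumed 30% elevated, 50% call rate and ICC 0.1–0.5. The t-test gave 4.8–6.1% and Mann-Whitney 4.7–6.1%.

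**The case against.** **Pooling is not stated.** A reader might infer that the plan commits to an invalid test. It does not. No section says that readings will be pooled, and the counts taken at the 7–10 day visit could equally give one total and one elevated count per woman. A per-woman percentage is continuous, and the t-test and Mann-Whitney in 2.4.2 would be valid for it. This stands, so the defect is an open choice rather than a planned error. It does not remove the point: 2.3.6 and 2.3.7 count readings, 2.3.1 refers the counts to the group, and the plan never makes the valid choice.

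**Outcome 2 might seem to need a reading-level model.** A woman with no elevated reading has no percentage, so a reader might infer that a per-woman analysis fails. It does not. She has a zero denominator and contributes nothing to GEE or a ratio estimator either. A per-woman test among women with at least one elevated reading keeps its level. Under either method the restriction depends on readings taken after randomization, and it should be stated.

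**The inflation could be put higher.** With 14 readings from every woman, DE is 2.3 at ICC 0.1 and 7.5 at ICC 0.5, giving errors of about 20% and 47%. That assumes complete recording, which the plan's 60% and 80% rates do not support.

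**Chance significance matters less for outcome 2.** In the monitoring arm, 2.3.1 has a nurse phone the provider after a high flag if the patient has not. A difference in calls is thus partly built into the intervention, and a true null is unlikely. This stands as far as it goes, but a pooled confidence interval for that difference would still be too narrow.

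**Conclusion.** The point holds as a conditional one. Outcomes 1 and 2 are defined on readings, and 2.4.2 gives neither a unit of analysis nor a method for repeated readings within a woman. If readings are pooled and tested as independent, the true error of a nominal 5% test is about 7–46% for outcome 1 and about 6–17% for outcome 2.

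The direction is certain for any positive ICC. The size rests on the assumed ICC, on 5–13 recorded readings (derived from the plan's schedule and recording rates) and on the assumed 2–3 elevated readings. The case is firm for outcome 1 at an ICC of about 0.1 or more. It is weaker for outcome 2 if elevated readings are few.

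The finding concerns 2 of 13 secondary outcomes, and these error rates say nothing about the primary comparison. It should be corrected before analysis, because the choice left open is between a valid and an invalid test and settling it costs almost nothing.

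**What to change.** Add a short statement to 2.4.2:

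1. For secondary outcomes 1 and 2, the woman is the independent unit.
2. Name one method in advance. Either:
   - one percentage per woman, compared by t-test (allowing unequal variances) or Mann-Whitney, with outcome 2 restricted to women with at least one elevated reading; or
   - a reading-level logistic GEE or ratio estimator with robust variance clustered on the woman.
3. Chi-squared and Fisher apply only to outcomes with one value per woman.
4. Report how many women in each group have no elevated reading and so do not enter outcome 2.

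Both options keep the error near 5%, but they estimate different things. The per-woman percentage gives each woman equal weight, so frequent recorders do not dominate. A ratio estimator, or GEE with independence working correlation, keeps the weighting by number of readings; clustering corrects only the standard error.

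The cost is a few sentences and standard software, with no new data. Confidence intervals will be wider than from a pooled analysis, and correctly so.

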2.2 Specific aims

Our objective is to trial RPM in the postpartum hypertensive population in a randomized control design, with an aim to increase the number of blood pressure measurements taken during the fragile and under-monitored postpartum period and to thereby improve postpartum blood pressure control and reduce severe morbidity and mortality.

Specific Aim 1. To compare the number of blood pressures recorded in the first 10 days postpartum between patients who have been enrolled in an RPM trial to those who are being treated with the usual care. We hypothesize that women using RPM will have more blood pressure values recorded at outpatient blood pressure assessment compared with patients using the usual care.

- **Sub-aim 1: To compare the percentage of elevated blood pressures that are discussed with an obstetric care provider between patients who have been enrolled in an RPM trial to those who are being treated with the usual care.** We hypothesize that women using RPM will communicate more frequently with their providers regarding elevated blood pressure values.
- **Sub-aim 2: To examine the effect of RPM on blood pressure control at 6 weeks in women with HDP.** We hypothesize that more women using RPM will be normotensive, defined as blood pressure < 140/90 mm Hg, at the end of the postpartum period, compared to those randomized to usual care.

Sub-aim 3: To compare time to outpatient initiation or adjustment of antihypertensive medications in women using RPM compared to the usual care. We hypothesize that women using RPM will have shorter time to initiation of medications or shorter time to change in medication regimen in the outpatient setting than those using the usual care.

Specific Aim 2. To compare rates of compliance with follow up visits between patients who have been enrolled in an RPM trial to those who are being treated with the usual care. We hypothesize that women using RPM will have a higher rate of compliance with outpatient blood pressure assessments and postpartum visits than patients using the usual care

- **Sub-aim 1: To analyze factors associated with poor postpartum follow up in both the study group and the control group.** We hypothesize that factors such as socioeconomic status, wait times at the office or clinic where care is provided, number of children at home, and educational level will be associated with lower follow-up rates.

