Measurements and surveys for patients in the study group will be scheduled in the eCC (see “HDP Calendar and Intervention Rules,” attached as a separate document to this IRB application). Data for patients in the study group will be transmitted to the Philips Clinical Call Center, staffed daily by nurses from 8am-8pm. The nurses will review measurements and survey results within 2 hours when they are flagged as high for attention. Criteria for flagging and therefore review by a nurse as well as for escalation to an obstetric provider is outlined in the workflow attached as separate documents to this IRB (“HDP calendar and intervention rules” / “Workflows”). If a measurement is flagged as high, the nurse will contact the patient and the patient’s provider (if the patient has not) by phone. The patient will also be automatically instructed via the system to call their provider immediately. If a measurement is flagged as low, the nurse will email the patient’s provider with a summary of the day’s measurements at the end of the day. If a patient does not enter measurements, the nurse will contact the patient directly. If the patient does not enter measurements for 3 consecutive days, the nurse will contact the patient’s provider, and will continue attempting to contact the patient daily. If a nurse cannot get in touch with the patient, the nurse will contact the patient’s provider. If a survey answer is flagged, the nurse will contact the patient and the patient’s provider (if the patient has not) by phone. The patient will also be automatically instructed via the system to call their provider immediately. If the patient does not answer a survey, the nurse will contact the patient the

following day. For all patients, regardless of whether or not they have flagged values, a weekly report of measurements will be generated and sent to the patient's providers every week.

Patients in both groups will be given an appointment to follow-up with their obstetric provider in the office at 7-10 days postpartum. Control group patients will be asked to bring a log of their recorded blood pressures to this visit. The number of measurements *total* and the number of measurements that were *elevated* will be ascertained for each group at this visit.

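### Provider contact per elevated reading is compared between arms with no named source, and nothing the plan describes collecting from controls captures it

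*Combined protocol and SAP*

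**What the plan says.** Three places commit the trial to this comparison.

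- Section 2.2, Specific Aim 1, Sub-aim 1: "To compare the percentage of elevated blood pressures that are discussed with an obstetric care provider".
- Section 2.3.6, secondary outcome 2: "Percentage of elevated blood pressures that triggered a phone call to an obstetric provider".
- Section 2.3.7, Communication: "Rate of communication between patient and obstetric provider for each abnormal blood pressure measurement will be compared between groups".

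None of them says where a contact is recorded, by whom or on what form, in either arm. The Blood pressures entry just before Communication in section 2.3.7 does name a source for each arm: the participant's own record for controls and eCC for the study group.

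For RPM women, section 2.3.1 describes a process: "Data for patients in the study group will be transmitted to the Philips Clinical Call Center, staffed daily by nurses from 8am-8pm". For a high flag, "the nurse will contact the patient and the patient’s provider (if the patient has not) by phone", and the system also prompts the woman to call. For a low flag the route is different: "If a measurement is flagged as low, the nurse will email the patient’s provider with a summary of the day’s measurements". Section 2.3.5 lists a part of the eCC user guide that covers "how these flags and issues are reviewed and addressed".

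For controls, section 2.3.1 says: "Control group patients will be asked to bring a log of their recorded blood pressures to this visit". Two quantities are then obtained at that visit in each group, the total number of measurements and the number elevated.

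**The concern.** The outcome needs a yes or no on provider contact for every elevated reading in both arms. In the RPM arm, someone other than the patient handles high-flagged readings as they occur and has reason to ask about contact. In the control arm nobody is described as asking, and the log and the visit counts do not hold the answer. A control contact that leaves no record would presumably be scored as no contact.

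The sub-aim's hypothesis is directional (RPM women will communicate more with their providers), and section 2.5 anticipates that result. If capture differs by arm, the expected result could appear with no true difference. It could also be masked if the error runs the other way. Analysis cannot restore contacts that were never recorded. The limitations in section 2.4.3 do not mention the issue.

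**Working it through.** **Step 1. The two arms side by side**

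| Item | RPM | Usual care |
|---|---|---|
| Source of readings | Transmitted to eCC | Self-kept log brought to the 7-10 day visit |
| Who sees a reading at the time | Call-centre nurse, if flagged | Nobody specified |
| Who asks whether the provider was contacted | Nurse, implicitly, for high flags | Nobody specified |
| Named source for outcome 2 | None | None |
| Obtained at the 7-10 day visit | Total and elevated counts | Total and elevated counts |

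Section 2.3.7 also collects home health visits and the blood pressures taken there, but not contacts. The surveys are attachments that were not available, and the plan does not say that they record contact per reading.

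**Step 2. The plan's own figures**

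The plan gives no figure for outcome 2 or Sub-aim 1, so there is none to reproduce. The only relevant numbers are the group sizes in section 2.4.1. For 60% against 80%, two-sided 0.05 (sidedness is not stated) and 80% power:

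n = [1.96·√(2·0.7·0.3) + 0.842·√(0.24 + 0.16)]² / 0.20² ≈ 81.2, which rounds up to 82. The arcsine method gives 80.3, which rounds up to 81. The plan's 81 is reproduced, and 81 × 1.25 = 101.25 gives its 101.

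**Step 3. Illustration: control contacts missed**

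Assumptions, none of them from the documents: the true contact rate c is the same in both arms, RPM capture is complete, a share s of control contacts is captured, and each woman has one elevated reading.

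Apparent control rate = c·s. Spurious gap = c·(1 − s).

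| c | s = 0.9 | s = 0.8 | s = 0.7 | s = 0.5 |
|---|---|---|---|---|
| 0.3 | 3 points | 6 | 9 | 15 |
| 0.5 | 5 | 10 | 15 | 25 |
| 0.7 | 7 | 14 | 21 | 35 |

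The chance of a false p < 0.05 favouring RPM is Φ{[d − 1.96·√(2p̄q̄/n)] / √[(p₁q₁ + p₂q₂)/n]}, where d is the spurious gap. For c = 0.5, s = 0.8 and n = 81, this is Φ{(0.100 − 0.153)/0.0778} ≈ 0.25.

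| n per arm | c = 0.5, s = 0.8 | c = 0.5, s = 0.5 |
|---|---|---|
| 50 | 17% | 74% |
| 81 | 25% | 92% |
| 101 | 30% | 96% |

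The row for 50 is included because not every woman need have an elevated reading, and section 2.1 presumes that only about half attend the 7-10 day visit.

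**Step 4. Illustration: selective logging in controls**

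The control denominator is also self-reported. Let l₁ be the chance that a reading which led to contact is in the log, and l₀ the chance for one that did not.

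Apparent control rate = c·l₁·s / [c·l₁ + (1 − c)·l₀].

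Take c = 0.5, l₁ = 0.9 and l₀ = 0.437. All are assumptions; the last borrows, purely as a convenient value, the recording rate cited in section 2.4.1. The denominator is 0.45 + 0.2185 = 0.6685.

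- s = 1: 0.45/0.6685 = 67%
- s = 0.8: 0.36/0.6685 = 54%
- s = 0.5: 0.225/0.6685 = 34%

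Against a true 50%, controls can therefore appear too high or too low.

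**The case against.** The strongest reply has four parts.

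1. A reader might infer that contact is documented for every elevated RPM reading. The documents do not say so. They describe nurse actions on flagged readings, and the flag criteria are in attachments that were not available. A low flag leads to an email, which is not the phone call in outcome 2. The clause that makes the nurse's call conditional does not say that the woman's own call is logged. The eCC line summarises a vendor guide and does not name eCC as the source for this outcome. This part stands: RPM capture may be incomplete too.

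2. A reader might infer that control contacts will be undercounted. That is a likely consequence, not one the documents establish. Step 4 shows how selective logging could reverse the direction. This stands.

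3. Equal true contact rates fit poorly with an intervention that itself generates calls to providers. This stands as a limit on Step 3, which shows only what unequal capture could do by itself.

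4. Section 2.3.7 is equally silent on sources for medication timing, readmissions and emergency visits. Chart extraction is already used at enrolment, and women not planning follow-up at the centre are excluded, so chart review in both arms is plausible. This stands only in part. It is not stated for contacts, and a phone conversation about one reading may leave no chart entry linked to that reading. The reading-level records that the plan does describe for controls hold no contact information.

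**Conclusion.** The point holds in a limited form. The plan names no source for provider contact in either arm, and nothing it describes collecting from controls captures it. High-flagged RPM readings go through a nurse who has to establish whether the woman has already called. Followed as written, capture is likely to differ by arm and probably favours RPM.

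The size is unknown. Under the assumptions of Step 3 the spurious gap runs from 3 to 35 points, for true rates of 30-70% and control capture of 50-90%. Step 4 shows that the error can also run against RPM. These are illustrations, not estimates, and it would be wrong to read any of them as the expected bias.

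This concerns one of 13 secondary outcomes and the sub-aim built on it; the primary outcome is untouched. It is worth correcting because, as planned, neither a positive nor a null result on this comparison could be interpreted with confidence.

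**What to change.** For each elevated reading, ask the same structured question in both arms, in the same way and at the same 7-10 day contact: was this reading discussed with an obstetric provider, when, and who initiated the contact? Ask by phone where the woman does not attend, since attendance is itself an outcome expected to differ by arm. Recording the initiator separates women's own calls from those made by the call centre.

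Supplement the answers with one review of provider and EHR telephone records, done identically in both arms. Compute outcome 2 and Sub-aim 1 from this common source, and report eCC and call-centre records separately. Adopt one definition of contact in place of the three terms now used (discussion, phone call, communication).

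Do not add a contact column to the control log alone. Prospective recording in one arm against recall in the other is not a common source, and the column could prompt controls to call.

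The cost is a short form item, a few follow-up calls, the record review, and recall error in both arms. The common question does not remove selective logging from the control denominator, so report the number of elevated readings and the number of women contributing them, by arm, beside the result.
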